16.2 Ethical Conduct of the Study

The investigational study will be conducted according to the Protection of Human Subjects (21 CFR [Code of Federal Regulations] 50), Institutional Review Boards (21 CFR 56), Obligations of Clinical Investigators (21 CFR 312.60 – 312.69), the current ICH Guideline for Good Clinical Practice (ICH E6), and all other applicable regulations.

16.3 Patient Information and Consent

The Investigator will obtain, document and retain IRB/IEC-approved written informed consent from the patient, as specified in [Section 9.1](#). Where required, the Investigator will use an appropriately translated and IRB/IEC-approved version. The Sponsor reserves the right to delay initiation of the study at a site where ICFs do not meet the standards of applicable local regulations or ICH E6.

Information should be given to the patient in both oral and written form, and patients must be given ample opportunity to inquire about details of the study. The ICF must be signed and dated by the patient, and by the person who conducted the discussion of the informed consent.

16.4 Patient Confidentiality

All laboratory specimens, evaluation forms, reports, and other records will be identified by a coded number. Clinical information will not be released without written permission of the patient, or the patient's legally authorized representation, except as necessary for monitoring by the relevant regulatory authorities, the Sponsor, or the Sponsor's representative. The

Investigator must comply with all local applicable privacy regulations regarding the protection of patient data.

16.5 Source Documents

Source data in a clinical study are the original records or certified copies where clinical observations are first recorded, which may include, but are not limited to, the patient's medical file, original laboratory reports, histology, and pathology reports (as applicable). The Investigator is responsible for maintaining adequate and accurate medical records from which accurate information will be entered into the eCRFs

16.6 Retention of Data

All essential documents, including eCRFs, source documents (regardless of media), and signed ICFs, should be retained by the Investigator, per the guidance in ICH E6 or other regulatory retention requirement. There may be other circumstances for which MacroGenics is required to maintain study records for longer periods; therefore, MacroGenics should be contacted before study records are removed from the control of the study site for any reason. The Investigator must obtain written permission from MacroGenics prior to destruction of study documents.

16.7 Sample Retention and Further Testing

Samples acquired for protocol-specified assays are retained for

- at least 1 year following the end of the study, and may be retained for
- up to 2 years after last approval of a marketing application in an ICH region or
- until there are no pending or contemplated marketing applications in an ICH region or
- until at least 2 years have elapsed since formal discontinuation of clinical development of the investigational product.

If the patient consents, or the patient's legal representative consents, to the use of their study samples for non-study research purposes, these samples may also be used for exploratory testing (including assay development) and may be retained up to 15 years from the end of study.

16.8 Financial Disclosure

The Investigator and Sub-Investigators will be required to disclose in writing any applicable financial arrangement as defined in US regulation. The Principal Investigator's disclosure will be signed and dated prior to participating in the study.

The information, as defined in 21 CFR 54, will be collected about the Investigators, their spouse and each dependent child. Investigators must update the Sponsor with any changes in reported information up to 1 year following the end of the study.

In accordance with Securities and Exchange Commission regulation (17 CFR 229.404), Investigators and Sub-Investigators must disclose if they are employees of MacroGenics, or if an immediate family member of a MacroGenics employee, officer, or director.

16.9 Publication and Disclosure Policy

Data collected in this clinical study belong to the study Sponsor. The publication terms regarding use of the study data will be noted in the Clinical Trial Agreement. This includes authorship: scheduling and prioritizing analyses for reports, publications, and presentations; and developing a review and approval process.

16.10 Discontinuation of the Study or Study Sites

Site participation may be discontinued by MacroGenics, the Investigator, a regulatory authority, or an IRB/IEC. The study may be discontinued by a regulatory authority or at the discretion of the Sponsor.

16.11 Identification of the Coordinating Principal Investigator

A Coordinating Principal Investigator will be appointed by the Sponsor Medical Monitor prior to the end of the study.

As part of his or her responsibilities, the Coordinating Principal Investigator will review the final clinical study report (CSR). Agreement with the final CSR will be documented by the dated signature of the Coordinating Principal Investigator.

Appendix 1 Time and Events Schedule

EVALUATION/ PROCEDURE	Screening D (-28 to -1)	Cycle 1					Subsequent Cycles		EOTV ^b	Follow- Up	
		D1	D2	D3	D8 (± 1d)	D15 (± 1d)	D1 (± 3d) ^a	End of Cycle			
Enoblituzumab + retifanlimab or tebotelimab		X						X			
Informed Consent (no time constraint)	X										
Inclusion/Exclusion Criteria	X										
Demographics	X										
Medical/Cancer History	X										
Tumor biopsy ^c	X								X		
Archival tumor specimen (no time constraint) ^e	X										
HPV p16 Status (no time constraint) ^d	X										
Enrollment	X										
Physical Examination ^e	X	X						X		X	
Height	X										
Weight	X	X						X		X	
ECOG Performance Status	X	X						X		X	
ECG (12-lead) ^f	X	X									
Vital Signs ^g	X	X						X		X	
Clinical Laboratory Tests ^h	X	X						X		X	
Coagulation ⁱ	X	X									
Urinalysis ^j	X	X						X			
Pregnancy Test ^k	X	X						X		X	
Tumor Assessment ^l	X								X	X	X
Pharmacokinetics											
ADA											
PBMCs, Serum, and Plasma for PD and Exploratory Biomarkers											
Concomitant Medications											
Concomitant Procedures											
Adverse Events											
Survival											X ^m

*In clinic visit for
PK/ADA/biomarker
assessments only*

See [Appendix 3](#)

See [Appendix 3](#)

See [Appendix 3](#)

EVALUATION/ PROCEDURE	Screening D (-28 to -1)	Cycle 1					Subsequent Cycles		EOTV ^b	Follow- Up
		D1	D2	D3	D8 (± 1d)	D15 (± 1d)	D1 (± 3d) ^a	End of Cycle		

- a A cycle is 21 days ± 3 days from the previous dosing day. There should be at least 18 days between administrations.
- b The EOTV, if conducted, should be performed within 30 days after the patient has met study treatment discontinuation criteria specified in [Section 4.4](#), and before initiation of any subsequent anticancer therapies.
- c All patients enrolled in this study must have an identified formalin-fixed, FFPE tumor specimen for assessment of PD-L1 status prior to study entry. If no archival specimen is available, tissue from a contemporaneous core or excisional biopsy is acceptable (fine needle aspirate is not sufficient). Patients must also be willing to provide consent for a baseline and on-treatment tumor biopsy (end of Cycle 2), if tumor lesions are accessible for biopsy with acceptable risk in the judgment of the Investigator and after discussion with the Sponsor. This requirement will expire after an adequate number of samples have been collected, as determined by the Sponsor. Submission of an archival sample is highly encouraged but not mandatory for patients that provide a fresh biopsy sample. Baseline biopsy to be obtained after confirmation of eligibility and before Cycle 1 Day 1. End of Cycle 2 biopsy to be obtained between 20 and 34 days after Cycle 2 dosing, and preferably before Cycle 3 Day 1 dosing. Cycle 3 Day 1 dosing should not be delayed beyond the window of 21 ± 3 days from the previous dosing day, unless there is another reason to delay dosing per [Section 4.3.1](#).
- d See [Section 9.9.2](#) for details.
- e Full physical examination at screening and EOTV, directed physical examination at other time points.
- f Cycle 1 Day 1 ECG is conducted prior to the first infusion of any study treatment and at the end (± 15 minutes) of the last study treatment infusion (retifanlimab, tebotelimab, or enoblituzumab, as applicable). Subsequent ECGs are obtained as clinically indicated. Screening and Cycle 1 Day 1 ECGs are performed in triplicate.
- g Vital signs are obtained within 15 minutes before the first infusion and within 10 minutes after the end of infusion of each study treatment (retifanlimab, tebotelimab, or enoblituzumab, as applicable), and as clinically indicated.
- h Includes hematology, serum chemistry, endocrine tests, and cardiovascular disease markers (see [Appendix 2](#)). Laboratory assessment samples may be collected up to 3 days in advance of Day 1 of all cycles. If the screening samples are collected within 3 days before Cycle 1 Day 1 these laboratory assessments do not need to be repeated on Cycle 1 Day 1.
- i Coagulation tests (see [Appendix 2](#)) performed at screening and Cycle 1 Day 1 (with a window of -3 days in relation to Day 1), then as clinically indicated.
- j Urinalysis (see [Appendix 2](#)) performed at screening, Day 1 of each cycle (with a window of -3 days in relation to the beginning of each cycle), and as clinically indicated.
- k Serum or urine pregnancy test for women of child-bearing potential (with a window of -3 days in relation to the beginning of each cycle).
- l Tumor assessments are performed at the end of Cycle 2 (with a window of -3 days in relation to the beginning of the next cycle), and at the end of every 3 cycles (Cycles 5, 8, 11, etc.) thereafter (with a window of -7 days in relation to the beginning of the next applicable cycle) until treatment discontinuation. Patients who discontinue from study treatment should be assessed every 12 weeks (± 1 week) after the EOTV (or, if no EOTV is conducted, after the decision to end treatment) until evidence of PD, initiation of another anticancer therapy, withdrawal of consent, LTFU, death, or 36 weeks after the last patient's EOTV. EOTV tumor assessment does not need to be conducted if prior tumor assessment was performed within 28 days of the EOTV and results are available for RECIST assessments. Patients who discontinue study treatment due to AEs are followed by radiographic evaluation until PD by RECIST v1.1, if the patients' condition allows. If not, patients will be followed for OS without radiographic evaluation upon the discussion with the Sponsor's Medical Monitor.
- m Survival follow-up occurs every 12 weeks (± 1 week) after the EOTV (or, if no EOTV is conducted, after the decision to end treatment) until withdrawal of consent, LTFU, death, or 36 weeks after the last patient's EOTV.

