Patients will receive the assigned study drugs (enoblituzumab 15 mg/kg and either retifanlimab 375 mg or tebotelimab 600 mg) on a Q3W basis, in cycles of 3 weeks duration (see [Figure 6](#)). The initial tumor assessment will occur at the end of Cycle 2 (i.e., after approximately 6 weeks), and at the end of every 3 cycles thereafter (i.e., approximately every 9 weeks). After receipt of the last dose of study treatment, patients will enter an Efficacy Follow-up Period and will be followed for survival.

Figure 6 Treatment Cycles

Study treatment will continue in cycles of 3 weeks duration until confirmed CR (except as noted below), disease progression, unacceptable toxicity, withdrawal of consent, physician recommendation to discontinue therapy, death, or the maximum allowed treatment duration has been reached (see [Section 4.4](#) for a complete list of reasons for discontinuation of treatment). The maximum allowed treatment duration is 35 cycles for each study drug.

Discontinuation of study treatment may be considered for patients who have attained a confirmed CR. However, until Cycle 33, 2 additional cycles of study treatment may be completed beyond the date of confirmed CR (the total number of cycles of study treatment must not exceed 35).

Patients who have radiographic progression may remain on study treatment until the next scheduled radiographic evaluation if the following conditions are met: absence of clinical symptoms or signs indicating clinically significant disease progression; no decline in ECOG performance status; absence of rapid disease progression or threat to vital organs or critical anatomical sites (e.g., central nervous system [CNS] metastasis, respiratory failure due to tumor compression, spinal cord compression) requiring urgent alternative medical intervention; and no significant, unacceptable, or irreversible toxicities related to study treatment.

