4.3.1 Dose Delays

Tebotelimab Cohort

Patients who experience a Grade 2 to 4 AE that is potentially dose-limiting should have study drug held pending assessment, management, and resolution of the AE. If the AE is assessed as unrelated to study drug or does not meet DLT criteria, therapy may be restarted at the previous dose and schedule, after appropriate recovery.

Retifanlimab and Tebotelimab Cohorts

A dose delay of up to 20 days is allowed for patients experiencing AEs. In the case of abnormal troponins or N-terminal pro b-type natriuretic peptide (NT-proBNP) values, study drug must be withheld and a thorough cardiac assessment performed promptly to diagnose myocarditis or other cardiovascular diseases; the patient may resume study drugs if myocarditis is not confirmed. Refer to [Section 7](#) for specific guidance on restarting study therapy for IRR and irAEs. A dose delay of up to 20 days may also be permitted for reasons other than AEs. All procedures at the missed dosing visit should be performed and treatment reinstated as if the delay had not occurred.

Patients with infusion delays > 20 days will discontinue the study drug, complete the End of Treatment visit, and then enter the Post-treatment Follow-up Period.

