11 ASSESSMENT OF EFFICACY

11.1 Efficacy Assessments

11.1.1 Disease Response Assessments

Tumor assessments will be obtained using CT and/or MRI scans and tumor response evaluated according to RECIST v1.1. Target and non-target lesions will be designated at screening and assessed at the end of Cycle 2 (i.e., after approximately 6 weeks, with a window of -3 days in relation to the beginning of the next cycle), and at the end of every 3 cycles thereafter (i.e., approximately every 9 weeks, with a window of -7 days in relation to the beginning of the next applicable cycle) until discontinuation of treatment. After receipt of the last dose of study treatment, all patients will enter an Efficacy Follow-up Period, during which tumor assessments will be obtained as described in [Section 9.13](#).

The overall responses will be categorized as Complete Response (CR), Partial Response (PR), Stable Disease (SD), Progressive Disease (PD), or Not Evaluable (NE). At each on-treatment tumor assessment time point, the objective response status will be determined. In the context of the statistical analysis for this trial, objective response determination and the assessment of best overall response (BOR) will be defined using RECIST v1.1 ([Appendix 4](#)).

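### On-treatment scans are scheduled by dosing cycle rather than by calendar, so dose delays can shift the scan dates and tend to bias the secondary PFS estimates upward when delays are frequent or long

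*Protocol*

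**What the plan says.** Protocol Section 11.1.1, the Synopsis and Appendix 1 (footnote l) give one rule. The first on-treatment scan is at the end of Cycle 2, with a window of -3 days from the next cycle. Later scans come "at the end of every 3 cycles (Cycles 5, 8, 11, etc.) thereafter", and each may be done up to 7 days before the following cycle starts. Footnote a of the same appendix defines the unit: "A cycle is 21 days ± 3 days from the previous dosing day". Section 4.1 describes the result as roughly 6 weeks and then roughly every 9 weeks.

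On delays, Section 4.3.1 states: "A dose delay of up to 20 days is allowed for patients experiencing AEs". The same limit applies to delays for other reasons, and no maximum number is given. It adds: "All procedures at the missed dosing visit should be performed and treatment reinstated as if the delay had not occurred".

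PFS is dated by documented progression or death (Protocol 14.6.3; SAP 5.1.2). It is reported as a Kaplan-Meier median and as rates at 6 and 12 months (SAP 6.7.2). SAP Table 2 censors an event that follows two or more consecutive missed scheduled assessments. After treatment ends, scans follow a calendar of every 12 weeks from the end of treatment visit (EOTV) (Protocol 9.13).

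**The concern.** If the dose that opens the next cycle is late, the scan window moves with it. Because each cycle is counted from the previous dose, every later scan stays shifted. Patients with toxicity are then scanned on a different grid from patients without it, and recorded PFS depends partly on dosing. There is no control arm to share the distortion, so it enters the absolute PFS median and the landmark rates directly. The censoring rule for missed scheduled assessments also has no fixed dates to count against.

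**Working it through.** **1. The plan's own timing.** First scan: 2 × 21 = 42 days = 6 weeks. Later interval: 3 × 21 = 63 days = 9 weeks. Both agree with Section 4.1, but only if no dose is late. One 20-day delay gives 63 + 20 = 83 days (11.9 weeks, +32%); two give 103 days (14.7 weeks); three give 123 days (17.6 weeks).

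**2. Distance to the landmarks.** If done on the day the next cycle starts, the Cycle 8 scan falls on study day 8 × 21 + 1 = 169 and the Cycle 17 scan on day 17 × 21 + 1 = 358. Six months is 182.6 days and 12 months is 365.25. Cumulative slips of 14 and 8 days respectively carry these scans past the landmark.

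**3. Direction for a single delay.** On a grid shifted by 20 days, a scan-detected progression is dated 20 days later, is unchanged, or is caught one scan sooner (63 - 20 = 43 days earlier). With exponential times and a true median of 3.2 months (the pembrolizumab figure in Protocol 2.2):
- Delay before the Cycle 5 scan: 56.8% later, 17.3% earlier, 25.9% unchanged. Mean = 0.568 × 20 - 0.173 × 43 = +3.9 days.
- Delay before the Cycle 2 scan: 72.8% later, 27.2% earlier. Mean = 0.728 × 20 - 0.272 × 43 = +2.8 days.

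**4. Six-month PFS.** Simulation of exponential PFS, with progression dated at the first scan after it occurs and independent delays per cycle. Delay rates are assumptions. Entries are calendar-anchored → cycle-anchored.

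| Delays | True median 10 weeks | True median 14 weeks |
|---|---|---|
| 7 or 14 days, 5% of cycles | 0.188 → 0.186 to 0.189 | 0.304 → 0.300 to 0.304 |
| 14 days, 10% | 0.188 → 0.200 | 0.307 → 0.316 |
| 14 days, 20% | 0.188 → 0.227 | 0.307 → 0.348 |
| 20 days, 20% | 0.188 → 0.269 | 0.307 → 0.389 |

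With 15% of events as exactly dated deaths, the last 14-week entry becomes 0.299 → 0.373, or +7.4 points.

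**5. Sensitivity to the scan day.** The table treats one 14-day delay as leaving the Cycle 8 scan just inside 6 months (168 + 14 = 182). If the scan is on the dosing day and the SAP's added day is counted, 169 + 14 = 183 and it crosses. On that footing (true median 3.2 months, 15% deaths), the calendar rate is 0.298. Cycle-anchored rates are 0.302 (7 days, 5%), 0.338 (14 days, 5%), 0.362 (14 days, 10%), 0.382 (14 days, 20%) and 0.370 (20 days, 20%). The 14-day excesses are therefore 4.0, 6.4 and 8.4 points. At the early edge of the window (day 162), even one 20-day delay gives day 182 and does not cross, so the extreme-case excess is smaller.

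**6. Median.** With calendar scans the recorded median is 105 / 30.44 = 3.45 months. The largest cycle-anchored value is 133 / 30.44 = 4.37 months (105 + 2 × 14 days), a difference of 0.92. With a true median of 14 weeks, 1 - 2^(-15/14) = 52.4% of events have occurred by Week 15. The recorded median therefore sits on that scan by a narrow margin and jumps when some patients' scans move.

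**7. DoR.** Assuming response at 14 to 90 days and a true median DoR of 12 months, one 20-day delay before the Cycle 2 or Cycle 5 scan changes mean DoR by -3 or -11 days. Before the Cycle 8 or Cycle 11 scan the change is about +2 days.

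**The case against.** The best textual defence is the Section 4.3.1 sentence on the missed visit, which can be read as keeping the original timing. It can also be argued that a 3-week cycle ends 21 days after its own dose even if the next dose is late. Neither settles the matter. The sentence concerns the dosing visit and does not name tumor assessments, which Appendix 1 lists in a separate end-of-cycle column with a window counted "in relation to the beginning of the next applicable cycle". On the second reading, the scan in the delayed cycle holds but all later scans still move. Scan timing during a delay is therefore unresolved, and sites could differ.

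The objection on size largely stands. The upper figure needs the maximum delay in 20% of cycles; over eight doses, 1 - 0.8^8 = 83% of patients would have at least one. The protocol reports related Grade 3 or higher events in 28.6%, 16.7% and 18.6% of patients in the enoblituzumab + pembrolizumab, enoblituzumab + retifanlimab and tebotelimab expansion data. These are not delay rates, but they do not suggest such an extreme.

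A reader might infer that every delay postpones detection, or that one 20-day delay adds 20 days to PFS. Step 3 shows otherwise. A reader might also infer that DoR is inflated, but its start is scan-dated too, so both ends can move.

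**Conclusion.** The point holds for PFS, as a tendency and not a certainty. The written rule lets scan dates follow dosing, and nothing clearly holds them in place. With rare delays the effect on 6-month PFS is negligible, except that 14-day delays matter if scans fall on the dosing day. With frequent or long delays it is several points, reaching about 7 to 8 in the extreme case. The median can move by up to about 0.9 months, mostly as a jump between scan dates, while the mean shift from a single delay is about 3 to 4 days. These sizes rest on exponential PFS, independent delays, assumed delay rates and the scan day within its window.

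The consequence is limited. PFS is secondary and descriptive, and neither document plans a formal comparison of PFS with historical figures. OS is dated by death, and the primary ORR and its sample size do not depend on scan dates in this way. The documents do not support reading this as a threat to the primary conclusion.

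**What to change.** In the Protocol Synopsis, Section 11.1.1 and Appendix 1 (footnote l), schedule on-treatment scans at Week 6 and then every 9 weeks (Weeks 15, 24, 33 and so on) from Cycle 1 Day 1, regardless of dose delays. The present windows refer to the next cycle and cannot simply be carried over. Restate them around the calendar dates, for example -3 days at Week 6 and -7 days thereafter. Reconcile the missed-visit sentence in Section 4.3.1 with this by saying explicitly what happens to tumor assessments during a delay.

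In SAP Section 5.1.2 and Table 2, define a missed scheduled assessment against that calendar while the patient is on treatment, and against the 12-weekly schedule from the EOTV afterwards.

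The cost is a wording change. It adds no scheduled scan time points and alters no dosing rule. The downside is that some scans will no longer coincide with a dosing visit.

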Appendix 2 Clinical Laboratory Tests

Pregnancy test: Blood or Urine Human chorionic gonadotropin (hCG)
 
Hematology: Hemoglobin Platelet count White blood cell count Absolute neutrophils, lymphocytes, eosinophils
 
Serum chemistry: Albumin Alkaline phosphatase Alanine aminotransferase Amylase Aspartate aminotransferase Bicarbonate Bilirubin (Total and Direct) Blood urea nitrogen Calcium Chloride Creatinine Gamma glutamyl transferase Glucose Lipase Magnesium Phosphate Potassium Sodium Uric Acid
	
Coagulation: Prothrombin time (PT) Activated Partial Thromboplastin Time (aPTT) INR Fibrinogen
 
Endocrine tests: Free thyroxine (T4) Thyroid-stimulating hormone
 
Urinalysis: Protein Occult blood
 
Cardiovascular disease markers Creatine phosphokinase N-terminal pro b-type natriuretic peptide Troponins

---	--

